14.2.4 Supplementary Analyses of the Primary Estimand

Supplementary analyses described in this section will be performed on all participants from Cohort B (parts 1 and 2 combined). Intercurrent events will be handled similarly to the primary estimand.

CONFIDENTIAL INFORMATION Summary statistics for the BICLA response will be summarized during the on-treatment period. The conditional treatment effect on BICLA response at Week 24 will be estimated using a logistic regression model with study intervention group and stratification factors.

Odds ratios and associated two-sided 95% Wald confidence intervals will be provided for each active group versus placebo and will be converted into differences to placebo and their 95% confidence intervals.

An additional supplementary analysis may be performed if 34 Cohort B participants or more (\sim 10 % of the planned sample size in Cohort B) are included in the FAS with no BILAG A score and less than 2 BILAG B scores at Baseline. If this threshold is reached, then the primary analysis described in Section 14.2.1 will be conducted on the subset of the FAS who had at least one BILAG A score and/or \geq 2 BILAG B scores.

This model assumes missing data are MAR.

[figure not shown]
The analysis will be conducted using all changes from Baseline in CLA-IGA observed up to Week 24 visit (see Section 9.7 for time windowing) in accordance with the treatment policy strategy for handling the intercurrent events. LS means for change from Baseline in CLA-IGA together with its 95% CIs will be presented by study intervention group and analysis visit, in a tabular and graphical form. The difference in the LS means between each study intervention group and placebo together with accompanying two-sided 95% CI will also be tabulated.

Cumulative distribution function for change score from Baseline at the visit of interest will be displayed by study intervention group to depict the treatment effect across the population.

14.3.2 Change in PGA of Cutaneous Lupus Disease Activity at Week 16 and Week 24

The physician's global assessment of cutaneous lupus disease activity is used to quantify disease activity and is measured using a 100 mm visual analog scale where 0 is "no cutaneous lupus disease activity" and 100 is "maximum cutaneous lupus disease activity". On a first version of the questionnaire, the length of the scale was 101.8 mm. All assessments collected from this incorrect version will then be corrected applying the following factor: *100/101.8. The corrected score will then be expressed on a 0-100 mm scale.

Attributes of the estimand are described in the table below.

Descriptive Analysis

PGA of cutaneous lupus disease activity and change score from Baseline will be summarized using standard statistics at Baseline and each on-treatment scheduled visit. A scatter plot of baseline values vs values at Weeks 16 and 24 by study intervention group will be presented for visualization purposes with the diagonal reference line (y=x) to be able to see potential shift.

Inferential Analysis

The same analysis as described for CLA-IGA in section 14.3.1 will be conducted: a MMRM will be fitted to model the change from Baseline in PGA of cutaneous lupus disease activity with study intervention group, analysis visit, treatment by analysis visit interaction as categorical variables, stratification factors (see Section 14), and baseline PGA of cutaneous lupus disease activity as a continuous covariate.

14.3.3 Clinically Meaningful CS Reduction by Week 12 and Sustained through Week 24

Analyses described in this section will be performed at the final analysis.

INFORMATION

Attributes of the estimands are described in the table below:

Endpoint	Clinically meaningful CS reduction, defined as reduction of daily prednisone-equivalent dose from ≥ 10 mg at Day 1 to ≤ 5 mg by the Week 12 visit and sustained through Week 24
Population(s)	 SLE participants (Cohort B) with daily prednisone-equivalent dose ≥ 10 mg at Day 1 Cohort A participants with daily prednisone-equivalent dose ≥ 10 mg at Day 1
Treatment	Enpatoran vs placebo
Population-level summary measure	Odds ratio (conditional on stratification factors) between each active dose and placebo

Clinically meaningful CS reduction at Week 12 will be assessed based on the "CORTICOSTEROID MEDICATION DETAILS" form. Sustainment of the reduction will be assessed throughout the period between Week 12 and Week 24 (see appendix 18.2 for derivation of daily prednisone-equivalent dose).

A composite estimand strategy will be applied to handle the intercurrent events. Participants who experience any of these intercurrent events will be considered as not achieving CS reduction.

Descriptive Analysis

The number and percentage of participants with a clinically meaningful CS reduction will be provided.

Inferential Analysis

A logistic regression of clinically meaningful CS reduction status (yes/no) on the study intervention groups as a categorical variable and the stratification factors (see Section 14) will be fitted.

Odds ratios together with their 95% CI will be provided for each enpatoran group vs placebo. Treatment effect (and 95% CI) on the probability scale will also be provided.

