Change from Baseline in the Skindex 29+3 symptom domain score at Week 24 Change from Baseline in the Skindex 29+3 Functioning and Emotion domain scores at Week 24 Change from Baseline in the Skindex 29+3 lupus-specific domain score at Week 24	MMRM analysis where score CFB at each visit through Week 24 is modeled, with terms for intervention group, visit, intervention group by visit interaction, Baseline score, and randomization stratification factors. Test and treatment effect estimator (with 95% 2-sided CI) based on difference (enpatoran versus placebo) in least squares means of Week 24 CFB from the model. Cumulative distribution function for Week 24 CFB will be estimated by intervention group. Missing data assumed to be missing at random (MAR), with missing data status noninformative for CFB. Descriptive statistics will be provided at each visit.	
The following secondary endpoints v Cohort A and Cohort B	vill be analyzed for CLE (active SCLE and/or DLE) and SLE participants from	
Clinically meaningful CS reduction, defined as reduction of daily prednisone-equivalent dose from ≥ 10 mg at Day 1 to ≤ 5 mg by the Week 12 visit and sustained through Week 24	This endpoint will be analyzed using the logistic regression model, with the covariates of the randomization stratification factors. Test and treatment effect estimator (with 95% 2-sided CI) will be based on the odds ratios (each enpatoran versus placebo) in participants with prednisone-equivalent dose ≥ 10 mg at Day 1. Descriptive statistics will be provided	

Enpatoran (M5049) The WILLOW study with enpatoran in SLE and CLE (SCLE and/or DLE) MS200569_0003

[figure not shown]
Endpoints	Statistical Analysis Methods
Change from Baseline in FACIT-Fatigue scores at Week 24	MMRM analysis where score CFB at each visit through Week 24 is modeled, with terms for intervention group, visit, intervention group by visit interaction, Baseline score, and randomization stratification factors. Test and treatment effect estimator (with 95% 2-sided CI) based on difference (enpatoran versus placebo) in least squares means of Week 24 CFB from the model. Cumulative distribution function for Week 24 CFB will be estimated by intervention group. Missing data assumed to be MAR, with missing data status noninformative for CFB.
	Descriptive statistics will be provided at each visit.
The following secondary endpoints w	vill be analyzed for SLE participants from Cohort B

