14.3.4 BICLA Response and Clinically Meaningful CS Reduction

This estimand will be analyzed at the final analysis. Its attributes are described in the table below:

Endpoint	BICLA response and clinically meaningful CS reduction, defined as reduction of daily prednisone-equivalent dose from ≥ 10 mg at Day 1 to ≤ 5 mg by the Week 12 visit and sustained through Week 24
Population(s)	SLE participants (Cohort B) with daily prednisone-equivalent dose ≥ 10 mg at Day 1
Treatment	Enpatoran vs placebo

Population-level	Odds ratio (conditional on stratification factors) between each active dose and placebo
summary measure	

A composite estimand strategy will be applied to handle the intercurrent events. Participants who experience any of these intercurrent events will be considered as non-responder.

Participants will be considered as responders if they have a BICLA response at Week 24 and a clinically meaningful CS reduction from ≥ 10 mg at Day 1 to ≤ 5 mg by the Week 12 visit sustained through Week 24 was observed (see section 14.3.3). If BICLA response is missing at Week 24, it will be considered as a non-response (see Section 14.2.1).

Descriptive Analysis

The number and percentage of participants with a BICLA response and a clinically meaningful CS reduction will be provided.

Inferential Analysis

A logistic regression of the BICLA response and clinically meaningful CS reduction status (yes/no) on the study intervention groups as a categorical variable and the stratification factors will be fitted.

Odds ratios together with their 95% CI will be provided for each enpatoran group vs placebo. Treatment effect (and 95% CI) on the probability scale will also be provided.

14.3.5 CLA-IGA 0 or 1 at Week 16 and Week 24

Estimands attributes are described in the table below.

Endpoint(s)	 Occurrence of CLA-IGA 0 or 1 at Week 16 Occurrence of CLA-IGA 0 or 1 at Week 24
Population(s)	 Cohort A Cohort B with CLASI-A ≥ 8 at Screening and confirmed at Day 1
Treatment	Enpatoran vs placebo
Population-level summary measure	Odds ratio (conditional on stratification factors) between each active dose and placebo

Descriptive Analysis

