LLDAS attainment will be summarized using descriptive statistics (frequency and percentage) at each on-treatment scheduled visit. Additionally, a line plot depicting the percentage of responders over time grouped by study intervention group will also be provided.

Inferential analysis

A logistic regression of LLDAS attainment (yes/no) at Week 24 on the study intervention groups as a categorical variable and the stratification factors will be fitted.

Odds ratios together with their 95% CI will be provided for each enpatoran group vs placebo. Treatment effect (and 95% CI) on the probability scale will also be provided.

INFORMATION

14.3.8 Remission Attainment through Week 24

This analysis will be conducted at the final analysis. Attributes of the estimand are described in the table below.

Endpoint	Remission attainment at Week 24
Population(s)	SLE participants (Cohort B)
Treatment	Enpatoran vs placebo
Population-level summary measure	Odds ratio (conditional on stratification factors) between each active dose and placebo

Remission attainment per 2021 DORIS definition (Vollenhoven 2021) is defined at a specific visit as meeting the following criteria at the visit:

- · CCI
- PGA of SLE < 0.5 (0-3 scale)
- Daily prednisolone-equivalent dose ≤ 5 mg from the day after the previous visit until the day of the current visit (see appendix 18.2 for derivation of daily prednisone-equivalent dose). If the previous visit is missed, the daily prednisolone-equivalent dose should be below or equal to 5 mg from 27 days prior to the current visit until that visit.
- Stable immunosuppressives including biologics

This criterion will not be specifically programmed but is covered via the handling of the intercurrent event "protocol-prohibited medications as determined by EAC".

Imputation for CCl is described in section 9.11.2 and section 9.11.4 respectively. If at least one criterion for remission is not evaluable at a visit, remission will be considered as non-attained at the visit.

Descriptive Analysis

Remission attainment will be summarized using descriptive statistics (frequency and percentage) at each on-treatment scheduled visit. Additionally, a line plot depicting the percentage of responders over time grouped by study intervention group will also be provided.

Inferential analysis

A logistic regression of remission attainment (yes/no) on the study intervention groups as a categorical variable and the stratification factors will be fitted.

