18.2.4 Corticosteroid usage, daily dose

Prednisone-equivalent daily dose (mg) by visit (post-baseline visits):

• Prednisone-equivalent CS daily dose is equal to the total dose (mg) the participant is receiving at the date of the scheduled visit + 1 day (using conversion rules specified in section 18.2.3). If several CS are taken at the same scheduled visit, then all CS doses should be added.

CS dosing at Baseline is defined at CS dose taken the day of baseline visit (Day 1).

Signature Page for VV-CLIN-324916 v4.0

Approval Task	PPD
	13-Dec-2024 10:00:07 GMT+0000

Signature Page for VV-CLIN-324916 v4.0

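### Cohort B models for corticosteroid reduction (SAP 14.3.3, 14.3.4) leave out the Day 1 steroid dose; adding it is a cheap improvement, with a power gain from nil to worthwhile depending on an association the documents do not give

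*SAP*

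**What the plan says.** The endpoint in SAP 14.3.3 is a fall in daily prednisone-equivalent dose from at least 10 mg at Day 1 to at most 5 mg by Week 12, held to Week 24. It is analysed in participants on at least 10 mg at Day 1, in Cohort B and separately in Cohort A ("Cohort A participants with daily prednisone-equivalent dose ≥ 10 mg at Day 1"). The model is "A logistic regression of clinically meaningful CS reduction status (yes/no) on the study intervention groups as a categorical variable and the stratification factors", and the summary measure is "Odds ratio (conditional on stratification factors) between each active dose and placebo". A treatment effect on the probability scale is also planned.

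SAP 14.3.4 uses the same covariates for the joint endpoint of BICLA response and steroid reduction, in Cohort B only. Protocol 9.4.1 agrees: "This endpoint will be analyzed using the logistic regression model, with the covariates of the randomization stratification factors".

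Day 1 dose is available. SAP 18.2.4 defines the baseline dose as the dose taken on Day 1, and SAP 12 summarises it by study intervention group, as a continuous variable and in bands. It is not named as a covariate in either model.

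**The concern.** The endpoint is a dichotomised change with one fixed target and very different starting points, so the required cut depends on the Day 1 dose. Elsewhere the plan adjusts for baseline: the CLASI-A ANCOVA (SAP 14.1.1) and the CLA-IGA MMRM (14.3.1) include the baseline value of their own outcome, and the Cohort B Part 1 logistic model for BICLA (14.2.1) includes a continuous baseline score. No reason is given for doing otherwise here.

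If Day 1 dose predicts success, leaving it out of a logistic model loses some power. It also leaves chance differences in starting dose between small groups in the reported odds ratios.

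**Working it through.** **No plan figure to reproduce.** The documents give no responder rate, subset size or power for this endpoint.

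**What the documents fix.**
- Day 1 dose in this population runs from 10 mg (SAP 14.3.3) to 30 mg (Protocol Appendix 7, Table 8). The cut needed to reach 5 mg is 10 − 5 = 5 mg up to 30 − 5 = 25 mg.
- In the example taper (Protocol Table 9), the 10 mg column reaches 5 mg at Week 8. The 30 mg column is at 12.5 mg at Week 8, 7.5 mg at Week 11 and 5 mg at Week 12.
- Cohort B strata other than region are blacked out. A split at 10 mg, the cut used for subgroups in SAP 8.2, would be constant in a population restricted to 10 mg or more.

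**Assumed, because the documents do not say.** Day 1 doses of 10/12.5/15/20/25/30 mg in 40/10/20/18/6/6% (mean 15.1 mg, SD 5.9 mg); responders 30% on placebo and 55% on the top dose; four equal arms; odds of success multiplied by a factor f per 5 mg of Day 1 dose.

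**Benchmark without covariates.** Power = Φ{[0.25 − 1.96·√(2·0.425·0.575/n)] / √[(0.30·0.70 + 0.55·0.45)/n]}. For n = 35 this is Φ{(0.25 − 0.2316)/0.1143} = 56.4%. For n = 50 it is Φ{(0.25 − 0.1938)/0.0957} = 72.2%.

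**Simulation 1.** Logistic model with treatment and region, without → with Day 1 dose. Wald test of top dose against placebo, one-sided 2.5%, 2000 runs per cell.

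| f per 5 mg | 20 per arm | 35 per arm | 50 per arm |
|---|---|---|---|
| 1.00 | 33.8 → 33.9% | 54.3 → 54.7% | 71.5 → 71.6% |
| 0.78 | 35.0 → 35.6% | 56.6 → 57.6% | 73.9 → 74.3% |
| 0.61 | 33.2 → 37.7% | 55.8 → 58.5% | 71.7 → 73.4% |
| 0.37 | 35.4 → 42.2% | 53.9 → 63.1% | 72.6 → 80.1% |

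The columns without adjustment for 35 and 50 per arm agree with the benchmark. The Monte Carlo standard error of one power figure near 50% is √(0.25/2000) = 1.1 points, so differences below a point should not be read. Type I error at 35 per arm was 2.0 to 2.7% without the dose and 2.2 to 3.1% with it.

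**Simulation 2.** 50 on 100 mg against 40 on placebo; doses as above but in 40/10/20/15/5/10%; placebo success 35%; 3000 runs; two-sided 5%.

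| f per 5 mg | Conditional OR 3.3 | Conditional OR 4.5 |
|---|---|---|
| 1.00 | 78.4 → 77.7% | 92.9 → 92.5% |
| 0.78 | 78.3 → 78.4% | 92.9 → 93.3% |
| 0.61 | 71 → 75% | 88 → 91% |
| 0.45 | 65 → 73% | 82 → 88% |
| 0.33 | 57 → 68% | 74 → 84% |

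A repeat with these settings gave +2 to +3 points at 0.61 and +6 to +13 at 0.45 to 0.33.

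**What those factors imply.** From 10 to 30 mg is four steps of 5 mg, so the odds of success at 30 mg relative to 10 mg are f⁴: 0.78⁴ = 0.37, 0.61⁴ = 0.14, 0.45⁴ = 0.041 (about 1/24), 0.33⁴ = 0.012 (about 1/84).

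**Chance imbalance.** The 95% range of the between-arm difference in mean Day 1 dose is ±1.96·5.9·√(2/n): ±3.7 mg at 20 per arm and ±2.8 mg at 35. At f = 0.61, a difference of that size moves the odds ratio by a factor of about 0.61^(−3.7/5) = 1.4 or 0.61^(−2.8/5) = 1.3.

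**Small subsets, as Cohort A may give.** With region and diagnosis in the model, 6 per arm was not estimable in 36 to 40% of runs without the dose and 41 to 47% with it. At 8 per arm the figures were 13 to 14% and 14 to 20%. There was no power gain at 4 to 8 per arm.

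**The case against.** The other side has good points, and most of them stand.

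- **Strength is not documented.** A reader might infer from Table 9 that Day 1 dose is a strong predictor. Table 9 is labelled as an example, investigators may depart from it, and every column is at 5 mg at Week 12. It shows different routes to the same status, not different success rates. The range of gains must therefore start at zero.
- **Nothing hinges on this power.** Protocol 9.4 treats secondary p-values as nominal, and no power is claimed for these endpoints.
- **The model matches its estimand.** The stated odds ratio is conditional on the stratification factors only. An odds ratio that also conditions on dose is a different quantity, because odds ratios are not collapsible. A reader might call the planned one biased; it is not.
- **Imbalance will be seen.** SAP 12 tabulates baseline dose by study intervention group. That shows an imbalance but does not adjust for it.
- **The shorter model has a benefit in sparse data.** A reader might say the term is left out for no benefit. The Cohort A-type results above contradict that.
- **Redaction.** A Cohort B stratum that carries dose at some other cut cannot be excluded. It would capture dose only in part.

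A reader might also extend the point to LLDAS ("A logistic regression of LLDAS attainment (yes/no) at Week 24", SAP 14.3.7) and remission (14.3.8), whose definitions contain a dose limit. The documents do not support that. Those models use all Cohort B participants, where a blacked-out 10 mg stratum would vary and could already adjust for dose.

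**Conclusion.** The point holds for Cohort B in SAP 14.3.3 and 14.3.4, as a cheap improvement and not as an error. The readable models omit a collected baseline value that sets the size of the cut required. The planned comparison remains valid, with no bias and no inflated type I error.

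The size rests wholly on the assumed association, dose mix, responder rates and subset size. Power changes by about zero for f of 1.0 to 0.78 per 5 mg, rises by about 2 to 4 points at 0.61, and rises by 6 points or more only at 0.45 or steeper, which means odds of success at 30 mg about 1/24 of those at 10 mg or less. The correction of chance imbalance is a further gain when dose matters. These figures are for the endpoint in 14.3.3; none was computed for the joint endpoint in 14.3.4.

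**What to change.** For Cohort B in SAP 14.3.3 and 14.3.4, before unblinding:

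1. Add daily prednisone-equivalent dose at Day 1 (SAP 18.2.4) as a continuous covariate.
2. Change the population-level summary row to an odds ratio conditional on stratification factors and Day 1 dose.
3. Keep the planned treatment effect on the probability scale.
4. State that the current model is used if the adjusted one cannot be estimated.

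Leave Cohort A, LLDAS and remission as they are.

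The cost is a few sentences in the SAP and one more parameter per model. The downside is that the reported odds ratio changes meaning, which step 2 makes explicit. Protocol 9.4 lets the analysis plan set out alternative or additional methods and asks for an amendment only when a principal feature changes; a covariate in a nominal secondary model should not need one. Adding the term after unblinding would look post hoc.

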14.3.4 BICLA Response and Clinically Meaningful CS Reduction

This estimand will be analyzed at the final analysis. Its attributes are described in the table below:

Endpoint	BICLA response and clinically meaningful CS reduction, defined as reduction of daily prednisone-equivalent dose from ≥ 10 mg at Day 1 to ≤ 5 mg by the Week 12 visit and sustained through Week 24
Population(s)	SLE participants (Cohort B) with daily prednisone-equivalent dose ≥ 10 mg at Day 1
Treatment	Enpatoran vs placebo

Population-level	Odds ratio (conditional on stratification factors) between each active dose and placebo
summary measure	

A composite estimand strategy will be applied to handle the intercurrent events. Participants who experience any of these intercurrent events will be considered as non-responder.

Participants will be considered as responders if they have a BICLA response at Week 24 and a clinically meaningful CS reduction from ≥ 10 mg at Day 1 to ≤ 5 mg by the Week 12 visit sustained through Week 24 was observed (see section 14.3.3). If BICLA response is missing at Week 24, it will be considered as a non-response (see Section 14.2.1).

Descriptive Analysis

The number and percentage of participants with a BICLA response and a clinically meaningful CS reduction will be provided.

Inferential Analysis

A logistic regression of the BICLA response and clinically meaningful CS reduction status (yes/no) on the study intervention groups as a categorical variable and the stratification factors will be fitted.

Odds ratios together with their 95% CI will be provided for each enpatoran group vs placebo. Treatment effect (and 95% CI) on the probability scale will also be provided.

14.3.5 CLA-IGA 0 or 1 at Week 16 and Week 24

Estimands attributes are described in the table below.

Endpoint(s)	 Occurrence of CLA-IGA 0 or 1 at Week 16 Occurrence of CLA-IGA 0 or 1 at Week 24
Population(s)	 Cohort A Cohort B with CLASI-A ≥ 8 at Screening and confirmed at Day 1
Treatment	Enpatoran vs placebo
Population-level summary measure	Odds ratio (conditional on stratification factors) between each active dose and placebo

Descriptive Analysis

The number and percentage of participants who have a CLA-IGA score of 0 or 1 ("clear" or "almost clear") will be provided at each scheduled visit. Participants experiencing an intercurrent event prior to the visit of interest will be considered as not having a CLA-IGA score of 0 or 1. A line plot depicting the percentage of responders over time grouped by study intervention group will also be provided.

Inferential Analysis

The same analysis as described in section 14.3.3 will be performed to assess the treatment effect on the occurrence of CLA-IGA 0 or 1 at Week 16 and Week 24.

Some CLA-IGA assessments have been conducted while Investigators were not trained. To assess the impact of the training on the results observed, descriptive and inferential analyses described in this section will be replicated using assessments collected on or after Investigator's training only.

14.3.6 SRI-4 Response through Week 24

This analysis will be conducted at the final analysis. Attributes of the estimand are described in the table below.

Endpoint	Systemic lupus erythematosus Responder Index-4 (SRI-4) response at Week 24
Population(s)	SLE participants (Cohort B)
Treatment	Enpatoran vs placebo
CCI	
Population-level summary measure	Odds ratio (conditional on stratification factors) between each active dose and placebo

The systemic lupus erythematosus responder index-4 (SRI-4) response is a measure of reduced SLE disease activity. A participant is an SRI-4 responder at a given time-point if they achieve:

- CC
- No worsening of ≥ 0.3 points in PGA of SLE disease activity score compared to Baseline (PGA score expressed on a 0-3 scale) AND
- No new BILAG A organ domain scores and ≤ 1 new BILAG B organ domain score compared to Baseline using BILAG 2004

Imputation of missing items will be performed for CCI, PGA of SLE disease activity and BILAG questionnaires as described in section 9.11. If SRI-4 response is still missing after imputation at a visit, the participant will be considered as a non-responder.

Descriptive Analysis

SRI-4 response will be summarized using descriptive statistics (frequency and percentage) at each ontreatment scheduled visit. The number and percentage of participants meeting each SRI-4 component

[figure not shown]
criterion will be provided during the on-treatment period. Additionally, a line plot depicting the percentage of responders over time grouped by study intervention group will also be provided.

Inferential analysis

A logistic regression of SRI-4 response at Week 24 on the study intervention groups as a categorical variable and the stratification factors will be conducted.

Odds ratio together with its 95% CI will be provided at Week 24 for each enpatoran group vs placebo. Treatment effect (and 95% CI) on the probability scale will also be provided. In addition, observed SRI-4 response (yes/no) will be summarized at each scheduled timepoint.

Subgroup analysis

14.3.7 LLDAS Attainment through Week 24

This analysis will be conducted at the final analysis. Attributes of the estimand are described in the table below.

Endpoint	LLDAS attainment at Week 24
Population(s)	SLE participants (Cohort B)
Treatment	Enpatoran vs placebo
Population-level summary measure	Odds ratio (conditional on stratification factors) between each active dose and placebo

Lupus low disease activity state (LLDAS) is attained at a specific visit if the following criteria are met at the visit (Golder 2020):

CCI

- o Renal, central nervous system, cardio-pulmonary: all descriptors of the system should be absent at the visit
- O Vasculitis: vasculitis descriptor of musculoskeletal system should be absent
- o Fever: fever descriptor of constitutional system should be absent
- No new descriptors of lupus disease activity compared with the assessment of the previous analysis visit

- PGA (scale 0-3) ≤ 1
- Daily prednisolone-equivalent dose \leq 7.5 mg from the day after the previous visit until the day of the current visit (see appendix 18.2 for derivation of daily prednisone-equivalent dose). If the previous visit is missed, the daily prednisolone-equivalent dose should be below or equal to 7.5 mg from 27 days prior to the current visit until that visit.
- Standard maintenance dosages of immunosuppressive drugs and approved biological agents

 This criterion will not be specifically programmed but is covered via the handling of the intercurrent event "protocol-prohibited medications as determined by EAC".

A composite estimand strategy will be applied to handle the intercurrent events: participants who experience any of these intercurrent events will be considered as not attaining LLDAS at all subsequent analysis visits.

Descriptive Analysis

LLDAS attainment will be summarized using descriptive statistics (frequency and percentage) at each on-treatment scheduled visit. Additionally, a line plot depicting the percentage of responders over time grouped by study intervention group will also be provided.

Inferential analysis

A logistic regression of LLDAS attainment (yes/no) at Week 24 on the study intervention groups as a categorical variable and the stratification factors will be fitted.

Odds ratios together with their 95% CI will be provided for each enpatoran group vs placebo. Treatment effect (and 95% CI) on the probability scale will also be provided.

INFORMATION

14.3.8 Remission Attainment through Week 24

This analysis will be conducted at the final analysis. Attributes of the estimand are described in the table below.

Endpoint	Remission attainment at Week 24
Population(s)	SLE participants (Cohort B)
Treatment	Enpatoran vs placebo
Population-level summary measure	Odds ratio (conditional on stratification factors) between each active dose and placebo

Remission attainment per 2021 DORIS definition (Vollenhoven 2021) is defined at a specific visit as meeting the following criteria at the visit:

- · CCI
- PGA of SLE < 0.5 (0-3 scale)
- Daily prednisolone-equivalent dose ≤ 5 mg from the day after the previous visit until the day of the current visit (see appendix 18.2 for derivation of daily prednisone-equivalent dose). If the previous visit is missed, the daily prednisolone-equivalent dose should be below or equal to 5 mg from 27 days prior to the current visit until that visit.
- Stable immunosuppressives including biologics

This criterion will not be specifically programmed but is covered via the handling of the intercurrent event "protocol-prohibited medications as determined by EAC".

Imputation for CCl is described in section 9.11.2 and section 9.11.4 respectively. If at least one criterion for remission is not evaluable at a visit, remission will be considered as non-attained at the visit.

Descriptive Analysis

Remission attainment will be summarized using descriptive statistics (frequency and percentage) at each on-treatment scheduled visit. Additionally, a line plot depicting the percentage of responders over time grouped by study intervention group will also be provided.

Inferential analysis

A logistic regression of remission attainment (yes/no) on the study intervention groups as a categorical variable and the stratification factors will be fitted.

Odds ratios together with their 95% CI will be provided for each enpatoran group vs placebo. Treatment effect (and 95% CI) on the probability scale will also be provided.

14.3.9 Change from Baseline in Tender and Swollen 28-joint Count through Week 24 – Cohort B

Attributes of the estimand are described in the table below. It will be analyzed at the final analysis.

Endpoint	Change in the number of joints which are tender and swollen in 28-joint count from Baseline at Week 24	
Population(s)	SLE participants from Cohort B	
Treatment	Enpatoran vs placebo	
Population-level summary measure	Mean difference between study intervention groups	

Descriptive Analysis

The following continuous variables will be summarized at Baseline and each on-treatment scheduled visit using descriptive statistics:

- Tender 28-joint count (raw and absolute change from Baseline)
- Swollen 28-joint count (raw and absolute change from Baseline)
- Tender and swollen 28-joint count (raw and absolute change from Baseline)

 Tender and swollen 28-joint count = count of joints which are both tender and swollen
- Number and percentage of participants who achieved ≥ 50 % reduction in baseline tender and swollen 28-joint count at each scheduled on-treatment visit

Inferential Analysis

An MMRM will be fitted to model the change from Baseline in the tender and swollen 28-joint count (count of joints which are both tender and swollen) with study intervention group, analysis visit, treatment by analysis visit interaction, stratification factors, and baseline tender and swollen joint count as a continuous variable. An unstructured correlation pattern will be used to estimate the variance-covariance of the within-subject repeated measures. The Kenward-Roger method will be used to estimate the

denominator degrees of freedom. Should the model fail to converge (including problems in estimating final Hessian matrix), then:

- A different structure for the variance-covariance matrix will be tested in the following order: Toeplitz, autoregressive (1), compound symmetry.
- In addition, the sandwich estimator of the standard error of the fixed effects parameters will be used as it can produce statistical inference more robust to variance-covariance pattern misspecification. In this alternative model, the between-within method will be used to estimate the denominator degrees of freedom.

[figure not shown]
This model assumes missing data are MAR.

The analysis will be conducted using all changes from Baseline in tender and swollen joint count observed up to Week 24 analysis visit (see Section 9.7 for time windowing) in accordance with the treatment policy strategy for handling the intercurrent events. LS means for change from Baseline in tender and swollen joint count together with its 95% CIs will be presented by study intervention group and analysis visit, in a tabular and graphical form. The difference in the LS means between each study intervention group and placebo together with accompanying two-sided 95% CI will also be tabulated.

Cumulative distribution function for Week 24 change from Baseline will be displayed by study intervention group to depict the treatment effect across the population.

14.3.10 Change from Baseline in Physician's Global Assessment of SLE at Week 24

Attributes of the estimand are described in the table below. It will be analyzed at the final analysis.

PGA of SLE disease activity will be analyzed using the score converted on a 0-3 scale (see Section 9.11.4).

Descriptive Analysis

PGA of SLE and change from Baseline in PGA will be summarized using descriptive statistics at Baseline and each on-treatment scheduled visit.

Inferential Analysis

An MMRM as described in section 14.3.9 will be fitted. It will use study intervention group, analysis visit, treatment by analysis visit interaction, stratification factors, and baseline PGA as a continuous variable.

LS means for change from Baseline in PGA together with its 95% CIs will be presented by study intervention group and analysis visit, in a tabular and graphical form. The difference in the LS means between each study intervention group and placebo together with accompanying two-sided 95% CI will also be tabulated.

Cumulative distribution function for Week 24 change from Baseline will be displayed by study intervention group to depict the treatment effect across the population.

14.3.11 Time to First Moderate/Severe BILAG Flare from Day 1 through Week 24

Attributes of the estimand are described in the table below.

Endpoint	Time to first moderate/severe BILAG flare from Day 1 through Week 24
Population(s)	SLE participants from Cohort B
Treatment	Enpatoran vs placebo
Population-level summary measure	Hazard ratio (conditional on stratification factors) between each active dose and placebo

A moderate flare is defined as at least two BILAG B organ scores due to items that are new or worse* in the month leading up to the current visit, when the participant does not meet the criteria for the severe flare.

A severe flare is defined as at least one BILAG A score in any organ systems due to one or more items that are new or worse*, in the month leading up to the current visit, compared to the participant's condition during the previous month.

[figure not shown]
*"Items that are new or worse" means that if the assigned grade A/B or C contains any item which is WORSE or NEW, such grade will be included into the flare consideration. This is valid for clinical organ domains. For laboratory organ domains (i.e., renal and hematological) where items are not classified as worse or new, there has to be an increase in score from B to A or C to B for flare to be considered.

All post-baseline BILAG assessments until Week 24 will be considered.

Time to first moderate/severe BILAG flare (weeks) will be derived as follows:

Time to first moderate/severe BILAG flare
= [min(Dates of visit with moderate/severe BILAG flare) - Date of randomization + 1]/7
The following censoring rules will be applied:

- Participants discontinuing the study prior to Week 24 without moderate/severe flare will have their time to first moderate/severe flare censored at the last visit at which flare could have been assessed (i.e., date of last BILAG assessment). Participants discontinuing the study prior to any post-baseline assessments will be censored at randomization date.
- Participants completing the 24-week treatment period without moderate/severe flare will have their time to first moderate/severe flare censored at Week 24.

Each stratum will define a separate baseline hazard function, i.e., for the i-th stratum the hazard function is expressed as: $h(i;t) = h(i,0;t) \exp(x\beta)$, where h(i,0;t) defines the baseline hazard function for the i-th stratum and x defines the study intervention group and β is the unknown regression parameter. Ties will be handled by replacing the proportional hazards model by the discrete logistic model.

The one-sided p-value from the stratified log rank test will be reported. This p-value should be considered as exploratory.

Results from an unstratified analysis will also be provided (HR together with its 95% CI and one-sided p-value from log rank test).

